9.9 Sample Size and Power Calculations

Pharmacodynamic (Primary): If the true SDs of the log₁₀ reduction from baseline in plasma HIV-RNA at 168 hours postdose are 0.3, 0.4, or 0.5 for this study, there is ~80% power to yield at least 70% posterior probability if the true mean log₁₀ reduction is at least 1.11, 1.12, or 1.13 log₁₀ with N=6 participants in a panel.

PK

Pharmacokinetic (Secondary): If the true SDs of the C_{168hr} triphosphate in PBMC are 0.25, 0.35, or 0.45 for this study, there is ~80% power to yield at least 70% posterior probability if the true mean C₁₆₈ are at least 0.27, 0.27, or 0.28 pmol/10⁶ cells with N=6 participants in a panel.

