9.3 Hypotheses/Estimation

Primary

At a dose that is sufficiently safe and generally well tolerated, MK-8527 has superior antiretroviral activity compared to placebo, as measured by change from baseline in plasma HIV-1 RNA (log₁₀ copies/mL) at 168 hours postdose. That is, the true mean difference in the plasma HIV-1 RNA reduction from baseline between MK-8527 and placebo is at least 1.0 log₁₀ copies/mL.

Secondary

At a dose that is sufficiently safe and generally well tolerated, the true GM C_{168hr} MK-8527-TP in PBMC is at least 0.2 pmol/10⁶ cells.

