9.6 Statistical Methods

Primary (Safety)

Incidence of AEs will be descriptively summarized. Summary statistics and plots will be generated for the change from baseline values in the VS, ECG parameter values, and selected laboratory safety parameter values for participants, as deemed clinically appropriate. Depending on the safety parameter, the difference from baseline will either be computed on the original scale (raw change from baseline) or on the log scale and backtransformed for reporting (percent change from baseline). Summary statistics for the raw laboratory safety tests, ECGs, and/or VS may also be computed, as deemed clinically appropriate.

Primary (Pharmacodynamics)

The log₁₀ plasma HIV-RNA (copies/mL) measurements from participants in all panels will be pooled and analyzed based on a longitudinal data analysis (LDA) model containing fixed effects for dose level, time (pre-dose, 168 hrs post-dose) and dose level by time interaction, and a random effect for participant. The response vector consists of the baseline and 168 hours post-baseline values. Time is treated as a categorical variable so that no restriction is imposed on the trajectory of means over time. The change from baseline for each dose level at 168 hours post-baseline will be estimated from this model. A posterior distribution for the true mean change from baseline at 168 hours will be generated for each dose level using flat priors under a normal likelihood assumption.

Historical placebo data from recent monotherapy studies in HIV-1 participants (MK-0518 Protocol 004, MK-1439 Protocol 005, MK-6186 Protocol 007, and MK-1972 Protocol 003) will be separately analyzed based on a longitudinal data analysis model containing fixed effects for study and time (pre-dose, 168 hrs post-dose), and a random effect for participant. The change from baseline for placebo at 168 hours post-baseline will be estimated from this model, and a posterior distribution for the true mean change from baseline at 168 hours will be generated using flat priors under a normal likelihood assumption. Using the posterior distributions for each dose level and placebo, the posterior distribution of the true mean difference between each dose level and placebo will be generated, and the posterior probability that the true mean difference in the log₁₀ plasma HIV-1 RNA reduction from baseline between MK-8527 and placebo is at least 1.0 log₁₀ copies/mL will be calculated.

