A 70% posterior probability for at least one dose level that also exhibits an acceptable safety and tolerability profile will satisfy the primary pharmacodynamics hypothesis. For each dose level, the posterior probability that the true mean log₁₀ plasma HIV-1 RNA reduction from baseline is at least 1.0 log₁₀ copies/mL will also be calculated. To address the exploratory objective related to antiretroviral activity at 672 hours post-baseline, a similar analysis will be performed using VL measurements at baseline and 672 hours post-baseline. Similar exploratory analyses may be performed at timepoints earlier than 168 hours post-baseline.

Secondary (Pharmacokinetic)

Values of MK-8527 plasma and intracellular MK-8527-TP in PBMC pharmacokinetic parameters C_{168hr}, C_{336hr}, C_{672hr}, AUC_{0-168hr}, AUC_{0-last}, AUC_{0-inf}, and C_{max} from participants in all panels will be pooled. Each PK parameter will be analyzed separately for plasma and PBMC. The PK log transformed and analyzed based on a linear model containing a fixed effect for dose level. The 95% confidence intervals for the means will be constructed on the natural log scale and will reference the t-distribution. Exponentiating the means will yield estimates for the population geometric means on the original scale. The secondary hypothesis will be evaluated by calculating the posterior probability that the true GM C_{168hr} MK-8527-TP in PBMC is at least 0.2 pmol/10⁶ cells for each dose level using flat priors under a normal likelihood assumption. The secondary hypothesis will be supported for any dose for which the posterior probability is greater than 70%. Data will be examined for departures from the assumptions of the statistical model(s) as appropriate; e.g., heteroscedasticity, nonnormality of the error terms. Distribution-free methods may be used if a serious departure from the assumptions of the model(s) is observed, or suitable data transformation may be applied.

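### Section 9.9 claims about 80% power per panel for the primary viral-load rule; with N=6 its own inputs give about 65%, 58% and 54%.

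*Combined protocol and SAP*

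**What the plan says.** Section 9.9 gives the primary pharmacodynamic power statement in one sentence. The SDs of the log10 reduction at 168 hours "postdose are 0.3, 0.4, or 0.5 for this study", and "there is ~80% power to yield at least 70% posterior probability if the true mean" log10 "reduction is at least 1.11, 1.12, or 1.13", in that order, "with N=6 participants in a panel".

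The rule to which this power refers is set elsewhere. Section 9.3 states the hypothesis that the true mean difference in HIV-1 RNA "reduction from baseline between MK-8527 and placebo is at least 1.0" log10 copies/mL. Section 9.6 obtains the posterior for each dose level and for historical placebo "using flat priors under a normal likelihood assumption". It declares success with "A 70% posterior probability for at least one dose level" that is also acceptably safe and tolerated. No placebo mean, SD or number of participants is given anywhere.

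**The concern.** Under a flat prior and normal likelihood, the amount by which the true mean must exceed 1.0 to give a fixed power is a multiple of the standard error, if placebo is taken as known. Between SD 0.3 and SD 0.5 that excess should grow by two thirds. In Section 9.9 it grows only from 0.11 to 0.13. That pattern suggests the three means do not come from the stated rule at N=6.

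This sentence is the only operating characteristic given for the primary pharmacodynamic hypothesis, in a trial meant to inform dose selection (Section 2.1). If the power is overstated, a dose with exactly the effect the protocol says it can detect will miss the 70% threshold much more often than the implied 20%. A reader relying on Section 9.9 could then take a missed threshold as stronger evidence of inadequate activity than it is.

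**Working it through.** **Inputs**
- SD of the change: 0.3, 0.4, 0.5; true mean: 1.11, 1.12, 1.13; N=6 per panel; stated power about 80% (Section 9.9).
- Target 1.0 log10 (Section 9.3); threshold 70%, flat prior, normal likelihood (Section 9.6).
- Placebo mean change: not given as a number. It is first taken as 0 and known. Section 4.2.1.3 says that placebo participants on average show no change beyond within-participant variability.

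**Formulas**

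The Section 9.6 model has categorical time and a dose-by-time interaction. With complete data, each panel's estimated change is therefore its own mean change, with SE = SD/√6. The posterior probability is at least 70% when the estimate exceeds 1.0 by at least z(0.70) × SE = 0.524 × SE. Hence:

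- Power = Φ[(mean − 1.0)/SE − 0.524]
- Mean needed for 80% power = 1.0 + (0.524 + 0.842) × SE = 1.0 + 1.366 × SE
- N needed at the stated mean = [1.366 × SD/(mean − 1.0)]²

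**Attempt to reproduce the stated 80%**

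| SD | SE | Stated mean | (mean − 1)/SE − 0.524 | Power | Mean needed for 80% | N needed at stated mean |
|---|---|---|---|---|---|---|
| 0.3 | 0.122 | 1.11 | 0.898 − 0.524 = 0.374 | 64.6% | 1.167 | 13.9 |
| 0.4 | 0.163 | 1.12 | 0.735 − 0.524 = 0.210 | 58.3% | 1.223 | 20.7 |
| 0.5 | 0.204 | 1.13 | 0.637 − 0.524 = 0.112 | 54.5% | 1.279 | 27.6 |

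The stated figure is not reproduced; the shortfall is 15 to 25 percentage points.

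**Other readings tried** (power for SD 0.3, 0.4, 0.5)

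| Reading | Power |
|---|---|
| t posterior, 5 df | 64.1%, 57.9%, 54.1% |
| t posterior, 25 df (SD pooled over five panels) | 64.5%, 58.3%, 54.4% |
| Means at the top of their rounding interval (+0.005) | 66.1%, 59.5%, 55.5% |
| Placebo estimated from an assumed 20 participants, same SD | 60.4%, 54.8%, 51.4% |
| Placebo estimated from an assumed 40 participants, same SD | 62.3%, 56.4%, 52.8% |
| Placebo viral load rises by an assumed 0.05 log10 | 78.3%, 69.7%, 64.0% |
| Placebo viral load rises by an assumed 0.10 log10 | 88.3%, 79.5%, 72.7% |
| Threshold 50% instead of 70% | 81.5%, 76.9%, 73.8% |
| SD read as per-measurement, within-participant correlation 0.8 | 81.5%, 73.8%, 68.5% |
| N=30 instead of 6 | 93.1%, 86.8%, 81.6% |
| Success in either of two equally effective panels | 87.5%, 82.6%, 79.3% |

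None gives about 80% in all three scenarios. With the assumed 40 placebo participants, the means needed for 80% become 1.0 + 1.366 × SD × √(1/6 + 1/40), that is 1.18, 1.24 and 1.30.

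**Could historical placebo data explain the flat pattern?** Let the placebo estimate have a fixed variance v, and let placebo viral load rise by r. The required mean is then 1.0 + 1.366 × √(SD²/6 + v) − r. For this to rise by only 0.02 between SD 0.3 and SD 0.5, the two square roots must differ by 0.02/1.366 = 0.0146. Their squares differ by (0.25 − 0.09)/6 = 0.0267, so they sum to 0.0267/0.0146 ≈ 1.82. The larger is therefore about 0.918, giving v ≈ 0.918² − 0.25/6 ≈ 0.80. That is a placebo SE of about 0.9 log10 with r = 1.366 × 0.918 − 0.13 ≈ 1.12 log10. Even allowing for rounding (a rise of 0.03), an SE of about 0.58 and a placebo rise of about 0.7 log10 are needed. Neither is credible for data pooled from four studies, or consistent with Section 4.2.1.3.

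**The case against.** The arithmetic is hard to contest, but four objections have substance.

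1. **The figures depend on a placebo mean the documents do not give.** A rise in viral load on placebo would increase power and a fall would reduce it. This stands as a condition on the figures. It does not rescue Section 9.9, because reaching 80% needs a different rise in each scenario: 0.167 − 0.11 ≈ 0.06, 0.223 − 0.12 ≈ 0.10 and 0.279 − 0.13 ≈ 0.15 log10.

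2. **Strict proportionality of the excess to the SD requires placebo to be known, or its variance to scale with the SD.** This is correct. The stated pattern is not impossible under every conceivable placebo input, but the inputs it needs are not credible.

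3. **Section 9.9 may refer to the reduction itself, not the difference from placebo.** Section 9.6 calculates a posterior for both, and Section 9.9 speaks of a mean reduction under a primary label. That the sentence leaves out placebo uncertainty is therefore an inference. Under the reduction-only reading, however, the 64.6%, 58.3% and 54.5% apply exactly.

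4. **The primary hypothesis needs only one successful dose level out of up to five panels, and nothing operational uses the power figure.** Power for the overall rule is higher if several doses work. But Section 9.9 speaks of N=6 in a panel, and that is the claim checked here. It is also true that panel decisions rest on safety, PK and viral-load data and that posterior probabilities are calculated for each dose level. Misreading a missed threshold is therefore a risk, not a certainty.

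**Conclusion.** The power statement in Section 9.9 is wrong as written. Per panel of six, under the plan's own rule and with placebo change taken as zero and known, power at the stated means is about 65%, 58% and 54%, not about 80%. A dose with the stated effect would miss the threshold in about 35% to 46% of cases instead of 20%. For 80% power the true difference must be about 1.17, 1.22 and 1.28 log10.

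Uncertainty in the placebo mean lowers power further, by about 2 percentage points with an assumed 40 placebo participants of the same SD. A rise on placebo would increase power, but no common rise restores the claim. The source of the stated means cannot be determined from the documents.

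**What to change.** Restate the primary pharmacodynamic sentence in Section 9.9 as a difference from placebo, per panel, in one of two ways:

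- With N=6, power is about 80% if the true difference is at least about 1.17, 1.22 or 1.28 log10 for an SD of 0.3, 0.4 or 0.5; or
- Keep 1.11, 1.12 and 1.13 as true differences and state power of about 65%, 58% and 54%.

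Either way, state the placebo mean, SD and number of participants assumed, and adjust the figures for the resulting placebo variance. As an illustration, 40 placebo participants of equal SD would move the first set to about 1.18, 1.24 and 1.30. If power for success in at least one panel is also wanted, give it separately with the assumed true effect in each panel.

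The cost is a change of SAP wording and a less favourable stated figure. N, dosing, the 70% rule and the analysis stay as they are.

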6.6 Dose Modification (Escalation/Titration/Other)

Prior to each intervention, the clinical and laboratory safety data, VL data, and PK data from the previous dose level will be reviewed by the investigator and discussed with the Sponsor to permit a decision on whether to advance to the next dosing level. No dose modification will occur without the joint agreement of the investigator and the Sponsor.

All dose escalation decisions will be made jointly by the investigator and the Sponsor. Each dose escalation decision will occur after at least 4 evaluable participants have completed the previous dose level.

Dose escalation decisions will be based on key safety data including VS, 12-lead ECGs, laboratory safety tests, and AEs from the previous dose levels up to at least 168 hours. Dose escalation in subsequent panels will also include review of PK data from previous panels. See Section 4.3. If, as judged by the Sponsor and investigator, the safety and tolerability data do not justify dose escalation, the dose will not be increased as planned. Instead, participants may:

- receive the same dose level to further explore safety and tolerability at that level;
- receive a lower dose of the study treatment;
- receive the same or lower dose as a divided dose; or
- receive a lower dose with or without food.

Or, dosing may be stopped. Participant discontinuation criteria are outlined in Section 7.

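### Section 9.9: the ~80% power for the secondary PK hypothesis does not follow from the Section 9.6 analysis with the SDs and means given

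*Combined protocol and SAP*

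**What the plan says.** - **Hypothesis (Section 9.3), in pmol/10⁶ cells.** For a dose with acceptable safety: "the true GM C_{168hr} MK-8527-TP in PBMC is at least 0.2".
- **Model (Section 9.6).** "The PK log transformed and analyzed based on a linear model containing a fixed effect for dose level".
- **Scale (Section 9.6).** The log in question is the natural one, as the sentence on interval estimates shows: "The 95% confidence intervals for the means will be constructed on the natural log scale". Means are exponentiated and reported as geometric means.
- **Posterior (Section 9.6).** The probability that the GM reaches 0.2 is obtained "for each dose level using flat priors under a normal likelihood assumption".
- **Decision rule (Section 9.6), threshold in percent.** "The secondary hypothesis will be supported for any dose for which the posterior probability is greater than 70".
- **Power (Section 9.9).** With N=6 in a panel and SDs of 0.25, 0.35 or 0.45 for the 168-hour triphosphate concentration, power to reach a 70% posterior probability is put at about 80% when the true means, in pmol/10⁶ cells, "are at least 0.27, 0.27, or 0.28". The section does not give the scale of the SDs. It speaks of a true mean where Sections 9.3 and 9.6 speak of a true GM.

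**The concern.** The same mean, 0.27, is printed for SD 0.25 and for SD 0.35 at the same power and the same N. If the listed SD is the only source of variance, the distance above 0.2 needed for a given power grows in proportion to the SD on the log scale, by a factor of 0.35/0.25 = 1.4. The two entries therefore cannot both be the mean that gives 80%.

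Section 9.9 is also the only place where the plan says what a panel of 6 can show on its one secondary hypothesis. Without the SD scale and the type of mean, a reader can neither check the claim nor reuse it. Across the readings of the SDs and means tried below, power at the printed means runs from about 46% to 99%.

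**Working it through.** **Inputs.** Threshold: GM of 0.2 (Sections 9.3 and 9.6). Rule: posterior probability above 70%, flat prior, normal likelihood (Section 9.6). Model: dose-level effect only, compared with a fixed threshold, so no placebo term enters. SDs 0.25, 0.35, 0.45; means 0.27, 0.27, 0.28; N=6; stated power about 80% (Section 9.9).

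**Formula.** With natural-log SD s and true GM m, the rule is met when (mean of ln C168 − ln 0.2)/(s/√6) exceeds z₀.₇₀ = 0.524. Hence

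power = Φ( ln(m/0.2)/(s/√6) − 0.524 ),

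and the GM needed for 80% power is 0.2·exp(1.366·s/√6), where 1.366 = 0.524 + 0.842.

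**Attempt to reproduce the stated ~80% (natural-log SD, GM).**

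| SD | Printed mean | s/√6 | ln(m/0.2) | Power | GM needed for 80% |
|---|---|---|---|---|---|
| 0.25 | 0.27 | 0.1021 | 0.3001 | Φ(2.416) = 99.2% | 0.230 |
| 0.35 | 0.27 | 0.1429 | 0.3001 | Φ(1.576) = 94.2% | 0.243 |
| 0.45 | 0.28 | 0.1837 | 0.3365 | Φ(1.307) = 90.4% | 0.257 |

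The stated figure is not reproduced.

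**Sensitivity on this reading.**
- Variance estimated from the panel, t posterior on 5 df: 99.1%, 93.9%, 90.0%. Simulation with 400,000 trials per scenario agrees.
- Rounding of the printed means (±0.005): 98.7–99.5%, 92.6–95.6%, 88.7–92.0%.
- Section 9.9 specifies N=6, but Section 6.6 allows escalation with fewer ("Each dose escalation decision will occur after at least 4 evaluable participants have completed the previous dose level"). At n=4, power is 97.0%, 88.3%, 83.4%.

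**Other readings of the SDs and means (N=6).**

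| Reading | Power at the printed means | Means needed for 80% |
|---|---|---|
| Natural-log SD, arithmetic means (GM = m/exp(s²/2) = 0.262, 0.254, 0.253) | 98.3%, 87.4%, 77.5% | 0.237, 0.258, 0.284 |
| Log10 SD, GM | 77%, 65%, 61% | 0.276, 0.313, 0.356 |
| Raw-scale SD | 56%, 49%, 46% | 0.339, 0.395, 0.451 |
| Listed values taken as log variances, GM | 83%, 76%, 76% | not computed |

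Reading the SDs as coefficients of variation gives 99%, 95%, 92% with GMs and 98%, 89%, 81% with arithmetic means. A two-sample standard error gives 94%, 83%, 78%. None of these gives about 80% in all three scenarios; a few match one scenario only.

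**What would reproduce the printed means.** Suppose a constant log-scale variance c is added to s²/6, so the needed GM is 0.2·exp(1.366·√(s²/6 + c)). With c = 0.0325 this gives 0.265, 0.274 and 0.284, which round to 0.27, 0.27 and 0.28. The match holds only for c of about 0.0321 to 0.0334. With N=6 that equals a second per-participant log-scale SD of √(6c), about 0.44 to 0.45. This component is an assumption: neither Section 9.6 nor Section 9.9 mentions one.

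**The case against.** The strongest reply is that this shows the figure cannot be traced, not that it is wrong. An extra variance component would recover all three printed means, and would explain why 0.27 appears twice. Table 4, which summarises geometric means and geometric CVs for the triphosphate and might show the variability the sponsor had in mind, is listed in the contents but is not in the text available for review. So an undisclosed input remains possible. That stands, and the correction should leave room for it. It does not rescue Section 9.9, which is unredacted and names no such component; nor does the Section 9.6 analysis contain one.

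A second reply is that Section 9.6 does not say how the variance is handled, so 99%, 94% and 90% are not the only possible values. With the panel's own variance, a flat prior on the SD (4 df) gives 98.9%, 92.9%, 88.6%, and a flat prior on the variance (3 df) gives 98.5%, 91.1%, 86.1%. This is fair as to the exact replacement figures, but every value is still above 80%.

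Third, the consequence is small, and the readings with power below the claim have little textual support because Section 9.6 specifies the natural log. Both points are accepted and are reflected in the rating.

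**Conclusion.** The concern holds, as a minor point. With the inputs printed in Section 9.9 and the analysis in Section 9.6, power is not about 80% in the three scenarios. If the SDs are natural-log, the means are GMs and nothing else contributes variance, power is about 99%, 94% and 90%, and the means that give about 80% are about 0.23, 0.24 and 0.26 rather than 0.27, 0.27 and 0.28. On that reading the discrepancy is conservative and N=6 is not undermined. On a log10 or raw-scale reading, power would fall short of the claim. The 70% rule works on the observed data and is unaffected on any reading. The conclusion that the figures do not reproduce rests on the listed SD being the only variance term.

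**What to change.** In Section 9.9, state the scale of the SDs, whether the means are geometric, how the variance is treated in the posterior, and any other variance component used. Then correct the figures:

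- If the SDs are natural-log, the means are GMs and there is no further component, either replace the means with 0.23, 0.24 and 0.26 pmol/10⁶ cells for about 80% power, or keep 0.27, 0.27 and 0.28 and state power of about 99%, 94% and 90%. These values assume a known variance; a t posterior on 5 df changes the power by less than half a point. If a flat prior is placed on the SD or the variance, recompute accordingly.
- If another scale or component was used, state it and recompute on that basis.

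The cost is SAP wording only. The analysis, the decision rule and the panel size do not change.

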10 SUPPORTING DOCUMENTATION AND OPERATIONAL CONSIDERATIONS

10.1 Appendix 1: Regulatory, Ethical, and Study Oversight Considerations

10.1.1 Code of Conduct for Clinical Trials

Merck Sharp and Dohme Corp., a subsidiary of Merck & Co., Inc. (MSD)

Code of Conduct for Interventional Clinical Trials

I. Introduction

A. Purpose

MSD, through its subsidiaries, conducts clinical trials worldwide to evaluate the safety and effectiveness of our products. As such, we are committed to designing, implementing, conducting, analyzing and reporting these trials in compliance with the highest ethical and scientific standards. Protection of participants in clinical trials is the overriding concern in the design of clinical trials. In all cases, MSD clinical trials will be conducted in compliance with local and/or national regulations (eg, International Council for Harmonisation Good Clinical Practice [ICH-GCP]) and in accordance with the ethical principles that have their origin in the Declaration of Helsinki.

B. Scope

Highest ethical and scientific standards shall be endorsed for all clinical interventional investigations sponsored by MSD irrespective of the party (parties) employed for their execution (eg, contract research organizations, collaborative research efforts). This Code is not intended to apply to trials that are observational in nature, or which are retrospective. Further, this Code does not apply to investigator-initiated trials, which are not under the full control of MSD.

II. Scientific Issues

A. Trial Conduct

1. Trial Design

Except for pilot or estimation trials, clinical trial protocols will be hypothesis-driven to assess safety, efficacy, and/or pharmacokinetic or pharmacodynamic indices of MSD or comparator products. Alternatively, MSD may conduct outcomes research trials, trials to assess or validate various endpoint measures, or trials to determine patient preferences, etc.

The design (ie, participant population, duration, statistical power) must be adequate to address the specific purpose of the trial. Participants must meet protocol entry criteria to be enrolled in the trial.

2. Site Selection

MSD selects investigative sites based on medical expertise, access to appropriate participants, adequacy of facilities and staff, previous performance in clinical trials, as well as budgetary considerations. Prior to trial initiation, sites are evaluated by MSD personnel to assess the ability to successfully conduct the trial.

3. Site Monitoring/Scientific Integrity

Investigative trial sites are monitored to assess compliance with the trial protocol and general principles of Good Clinical Practice (GCP). MSD reviews clinical data for accuracy, completeness, and consistency. Data are verified versus source documentation according to standard operating procedures. Per MSD policies and procedures, if fraud, scientific/research misconduct, or serious GCP-noncompliance is suspected, the issues

are investigated. When necessary, the clinical site will be closed, the responsible regulatory authorities and ethics review committees notified.

B. Publication and Authorship

Regardless of trial outcome, MSD commits to publish primary and secondary results of its registered trials of marketed products in which treatment is assigned, according to the prespecified plans for data analysis. To the extent scientifically appropriate, MSD seeks to publish the results of other analyses it conducts that are important to patients, physicians, and payers. Some early phase or pilot trials are intended to be hypothesis-generating rather than hypothesis testing, in such cases, publication of results may not be appropriate since the trial may be underpowered and the analyses complicated by statistical issues such as multiplicity.

MSD's policy on authorship is consistent with the recommendations published by the International Committee of Medical Journal Editors (ICMJE). In summary, authorship should reflect significant contribution to the design and conduct of the trial, performance or interpretation of the analysis, and/or writing of the manuscript. All named authors must be able to defend the trial results and conclusions. MSD funding of a trial will be acknowledged in publications.

III. Participant Protection

A. Ethics Committee Review (Institutional Review Board [IRB]/Independent Ethics Committee [IEC])

All clinical trials will be reviewed and approved by an IRB/IEC before being initiated at each site. Significant changes or revisions to the protocol will be approved by the ethics committee prior to implementation, except changes required urgently to protect participant safety that may be enacted in anticipation of ethics committee approval. For each site, the ethics committee and MSD will approve the participant informed consent form.

B. Safety

The guiding principle in decision-making in clinical trials is that participant welfare is of primary importance. Potential participants will be informed of the risks and benefits of, as well as alternatives to, trial participation. At a minimum, trial designs will take into account the local standard of care.

All participation in MSD clinical trials is voluntary. Participants enter the trial only after informed consent is obtained. Participants may withdraw from an MSD trial at any time, without any influence on their access to, or receipt of, medical care that may otherwise be available to them.

C. Confidentiality

MSD is committed to safeguarding participant confidentiality, to the greatest extent possible. Unless required by law, only the investigator, Sponsor (or representative), ethics committee, and/or regulatory authorities will have access to confidential medical records that might identify the participant by name.

D. Genomic Research

Genomic research will only be conducted in accordance with a protocol and informed consent authorized by an ethics committee.

IV. Financial Considerations

A. Payments to Investigators

Clinical trials are time- and labor-intensive. It is MSD's policy to compensate investigators (or the sponsoring institution) in a fair manner for the work performed in support of MSD trials. MSD does not pay incentives to enroll participants in its trials. However, when enrollment is particularly challenging, additional payments may be made to compensate for the time spent in extra recruiting efforts.

MSD does not pay for participant referrals. However, MSD may compensate referring physicians for time spent on chart review to identify potentially eligible participants.

B. Clinical Research Funding

Informed consent forms will disclose that the trial is sponsored by MSD and that the investigator or sponsoring institution is being paid or provided a grant for performing the trial. However, the local ethics committee may wish to alter the wording of the disclosure statement to be consistent with financial practices at that institution. As noted above, all publications resulting from MSD trials will indicate MSD as a source of funding.

C. Funding for Travel and Other Requests

Funding of travel by investigators and support staff (eg, to scientific meetings, investigator meetings, etc.) will be consistent with local guidelines and practices.

V. Investigator Commitment

Investigators will be expected to review MSD's Code of Conduct as an appendix to the trial protocol, and in signing the protocol, agree to support these ethical and scientific standards.

